5.6.6 Other Safety Analyses

No other safety analyses are planned for this study.

5.7 Other Analyses

No other analyses are planned for this study.

6 INTERIM ANALYSES

No interim analyses are planned for this study.

7 CHANGES IN THE PLANNED ANALYSES

A summary of all major additions, changes and deletions in the planned analyses described in the protocol will be provided in this section.

There was a major addition.

- Add the description of statistical analysis and data handling if the primary endpoint is successfully achieved according the protocol amendment ([section 3](#)).

There were minor additions, changes and deletions other than the above.

- Summarization of “The percent change in seizure frequency of POS per 28 days” has been changed to per 12 weeks from per 28 days because considering baseline collection period in the clinical study protocol (section 5.1.3 and 5.4.3).
- Summarization of “Treatment Compliance” has been added (section 5.2.6).
- Summarization of “The number (percentage) of subjects with POS who achieved seizure-free during the 52-week treatment of 4 mg (ie, 26-week Maintenance Period of 4 mg and 26-week Extension Phase)” has been added (section 5.4.3).
- Summarization of “The number (percentage) of subjects with POS who achieved seizure-free during the entire study period and the corresponding 95% confidence interval (CI)” has been added (section 5.4.3).
- Summarization of “TEAEs by SOC and PT by period, and by dose” has been added (section 5.6.2).
- Summarization of “TEAEs of special interest” has been added (section 5.6.2).
- Summarization of “the actual value and the change from baseline to each postbaseline visit by visit” has been changed to “the actual value and the change from baseline to end of treatment will be summarized” (section 5.4.3).
- Summarization of “shift tables that compare the baseline LNH classification to the LNH classification at each postbaseline visit” has been deleted (section 5.4.3).
- Summarization of “Summary statistics for vital signs parameters and weight, and changes from baseline will be presented by visit” has been changed to “Summary statistics for vital signs parameters and weight, and changes from baseline to end of treatment will be presented” (section 5.6.4).
- Summarization of “Shift tables will present changes from baseline in ECG interpretation by visit” has been changed to “Shift tables will present changes from baseline to end of treatment in ECG interpretation” (section 5.6.5).
- The cases when the plasma perampanel concentration data will be excluded from the calculation of summary statistics have been added (section 5.5.1).
- “The relationship between plasma concentrations of perampanel at steady state and seizure free status will be analyzed graphically.” has been added (section 5.5.1.1).
- “Plasma perampanel concentration data at Early transition visit or Early discontinuation visit will not be included in tables and figures for pharmacokinetic analysis.” has been added (section 5.5.1).
- “Summarization of plasma concentrations for perampanel at the 4 mg Maintenance Period and at the 8 mg Maintenance Period” has been changed to “Summarization of plasma concentrations for perampanel at the 4 mg Treatment Phase and at the 8 mg Treatment Phase” (section 5.5.1.1).

- Summarization of “seizure-free rate, time to first seizure onset and time to withdraw from study during the 52-week maintenance period of 4 mg and the 52-week maintenance period of the last evaluated dose by country” has been added (section 5.4.3).
- Summarization of “seizure-free rate during the 26-week maintenance period of 4 mg and the 26-week maintenance period of the last evaluated dose by medical history of simple partial seizure type” has been added (section 5.4.3).

8 DEFINITIONS AND CONVENTIONS FOR DATA HANDLING

The data will be handled as follows. The sponsor will determine how to handle all data prior to data base lock.

8.1 General Data Handling

Definition of Baseline data

Baseline is defined as the last non-missing value observed on or prior to the first study drug dispensing date.

Definition of Change from Baseline, Percent Change from Baseline

- Change from baseline = Post-baseline value - Baseline value
- % Change from baseline = (Change from baseline / Baseline value) * 100

For any baseline value of 0, the subject’s corresponding percent change from baseline will not be included in the summary statistics table.

Handling of data not within specified periods or within the follow-up period

Data obtained in the Follow-up Phase except for AE, Duration of Exposure and TEMAV will not be included in the summary tables. These data will be presented in the subject data listing.

Definition of End of Treatment

End of treatment phase during the 26-week Maintenance Period of the last evaluated dose is defined as the closest value observed on or post to the disposition date in the 26-week Maintenance Period of the last evaluated dose. If there is no adequate data, the closest value observed prior to the disposition date is selected.

End of treatment during the entire study (treatment phase or extension phase) is defined as the closest value observed on or post to the last disposition date in the entire study. If there is no data, the closest value observed prior to the last disposition date is selected.

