Median, Q1 and Q3 time to withdraw from the study will be estimated by Kaplan-Meier method by country. The cumulative probability of the event (ie, withdraw from the study) at every 26 weeks will also be calculated by country. Corresponding 2-sided 95% CIs will also be presented by country. The Follow-up Phase will not be the period to be analyzed. The above analysis will be summarized for the entire study period of 4 mg and the entire study period of the last evaluated dose, respectively.

The number (percentage) of subjects with POS who achieved seizure-free during the 26-week Maintenance Period of 4 mg and the 26-week Maintenance Period of the last evaluated dose, and each corresponding 95% CI will be calculated by Medical History of Simple Partial Seizure Type.

The percent change in seizure frequency of POS per 12 weeks in the Maintenance Period of the last evaluated dose and Extension Phase relative to the baseline will be summarized, respectively. The derivation of seizure frequency will be defined in the [section 8](#).

The change in EQ-5D-5L measurements from baseline to each postbaseline (ie, the Treatment Phase and the Extension Phase) visit, end of treatment phase (the 26-week Maintenance Period of the last evaluated dose) and end of treatment (the entire study of the last evaluated dose) will be summarized.

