Study days during the post-baseline of maintenance period will be the period between the date of study drug dispensing for the Maintenance Period of the last evaluated dose and the disposition data in maintenance period of the last evaluated dose. Study days during the post-baseline of extension phase will be the period between the disposition data in maintenance period of the last evaluated dose and the date of data cutoff or the date of study discontinuation, whichever comes first.

the data on seizure expression that obtained during the Titration Period and the Follow-up Phase will be presented only in the subject data listing.

Handling of missing data

- **Seizure frequency**

If subjects have a missing seizure count in any of each seizure type (ie, simple partial with motor signs, simple partial without motor signs, complex partial, and complex partial with secondarily generalized seizure) for each unique diary record, the overall seizure frequency for that record will be handled as missing data. Similarly, if complex partial and/or complex partial with secondarily generalized seizure are missing for each unique diary record, then complex partial seizure plus secondary generalized seizure frequency will be handled as a missing data.

- **EQ-5D-5L**

No imputation will be performed for the missing value.

Censoring rules for time to event analysis

1. The censored rule for the analysis of time to first seizure onset will be provided in the following table. If subjects met multiple censoring criteria, the censoring date will be the earliest date of them.

No.	Situation	Date of Event or Censoring	Outcome
1	Seizure onset	Date of the first seizure onset	Event
2	Withdraw from the study	Date of study withdrawal	Censored
3	Ongoing at the data cutoff (with no seizure)	Date of data cutoff (each subject's final non-missing assessment date)	Censored

2. The censored rule for the analysis of time to study withdrawal will be provided in the following table. If subjects met multiple censoring criteria, the censoring date will be the earliest date of them.

No.	Situation	Date of Event or Censoring	Outcome
1	Withdraw from the study	Date of study withdrawal	Event
2	Ongoing at the data cutoff	Date of data cutoff (each subject's final non-missing assessment date)	Censored

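### The SAP's end-of-treatment-phase fallback has no lower bound, so for EQ-5D-5L it can select a value from before the Maintenance Period, in conflict with the SAP's no-imputation rule

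*SAP*

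**What the plan says.** SAP 5.4.3 summarises the change in EQ-5D-5L at each post-baseline visit and at two derived time points: "end of treatment phase (the 26-week Maintenance Period of the last evaluated dose) and end of treatment (the entire study of the last evaluated dose").

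SAP 8.1 defines both. The end-of-treatment-phase value "is defined as the closest value observed on or post to the disposition date in the 26-week Maintenance Period of the last evaluated dose". Failing that, "If there is no adequate data, the closest value observed prior to the disposition date is selected". The entire-study value has a parallel fallback: "If there is no data, the closest value observed prior to the last disposition date is selected".

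The same section fixes the two terms of the change score. "Baseline is defined as the last non-missing value observed on or prior to the first study drug dispensing date", and "Change from baseline = Post-baseline value - Baseline value".

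For EQ-5D-5L specifically, SAP 8.2 states under missing data: "No imputation will be performed for the missing value". SAP 8.3 applies essentially the same selection rule to laboratory values, vital signs and ECGs, and there calls it imputation by last observation carried forward.

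The EQ-5D-5L schedule is in Protocol Section 9.5.2:
- **Table 3 (4 mg):** Visit 1, Visit 9 and the early discontinuation visit.
- **Table 4 (8 mg):** Visit 2a, Visit 9a, the early transition visit and the early discontinuation visit.
- **Table 5 (Extension):** Visit 13, with further marks at the early discontinuation and end-of-study visits.

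**The concern.** A rule that looks backward for the nearest earlier value does little harm when an assessment is repeated often, because the earlier value is then usually recent and on the same dose. EQ-5D-5L is not repeated in that way. It is taken before a Maintenance Period and again when that period closes, with nothing scheduled between. If the closing assessment is absent, the backward search passes through the whole Maintenance Period and stops at a value that belongs to another part of the study.

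Such a value would be tabulated as the end of the treatment phase at the last evaluated dose although it was measured before Maintenance on that dose began. The End of Treatment minus Baseline change in EQ-5D-5L is a named exploratory objective (Protocol 8.3, SAP 3.1.3). One programmer following 8.1 and another following 8.2 could report different numbers of subjects and different means for it.

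**Working it through.** The plan gives no figure to reproduce here. The check sets the selection rule against the visit schedule.

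**1. EQ-5D-5L assessments inside Maintenance, before its closing visit.** Table 3, Visits 4 to 8: none. Table 4, Visits 4a to 8a: none.

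**2. How far back the fallback reaches if the closing value is missing.**
- 8 mg: Visit 2a is Day 1 of 8 mg titration, 8 mg Maintenance starts on Day 29 and Visit 9a is Day 211. Visit 2a is therefore 29 − 1 = 28 days before Maintenance starts and 211 − 1 = 210 days before its scheduled close.
- 4 mg: Visit 1 is no later than Day 1 and Visit 9 is Day 225, a gap of at least 225 − 1 = 224 days, and up to four weeks more because screening may begin at Day −28. Visit 1 is the only scheduled EQ-5D-5L up to first dispensing, so it is the baseline under 8.1. Used as the outcome, it gives a change of exactly 0.

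**3. The treatment-phase rule applied literally to illustrative subjects.**

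| Subject | Value selected | Step used |
|---|---|---|
| 8 mg, closing value not done, no later value | Visit 2a | fallback |
| 8 mg, closing value and Visit 2a not done, no later value | Visit 1, change 0 | fallback |
| 4 mg, Visit 9 not done, no later value | Visit 1, change 0 | fallback |
| 4 mg, early discontinuation visit Day 120, disposition Day 134 after a taper | Day 120 value | fallback |
| 4 mg, Visit 9 done Day 222, disposition Day 225 | Visit 9 | fallback |
| 4 mg, Visit 9 not done, Visit 13 done | Visit 13, which is 183 − 1 = 182 days into the Extension Phase | first step, read with no upper limit |

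The first three rows show the defect. Rows four and five show the fallback working properly. The last row shows that the first step has no upper bound.

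**4. The two rules side by side.** Section 8.1 fills the time point from an earlier visit, whereas 8.2 leaves a missing EQ-5D-5L missing. Section 8.3 describes the 8.1 type of selection as imputation. Nothing in the SAP ranks one rule above the other for EQ-5D-5L.

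**5. Subjects still on 8 mg at the primary-endpoint analysis.** Under Protocol 9.7.1.6.4 and SAP Section 3, if the primary endpoint is met, subjects still in the 8 mg Treatment Phase are analysed up to their latest visit and later data count as Extension data. Before Visit 9a, such a subject's only scheduled 8 mg EQ-5D-5L is Visit 2a, unless the subject transitions or discontinues early. The SAP gives no disposition date for these subjects. If the analysis cut stands in for it, the fallback selects Visit 2a.

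**The case against.** Four arguments on the other side have weight.

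- **The fallback is often right.** It is triggered by timing relative to the disposition date, not only by a missing assessment. Drug may be dispensed for a taper at early discontinuation, and Protocol 9.3.3 dates discontinuation at complete withdrawal of perampanel when other antiepileptic drugs are needed. The SAP does not define the disposition date. If it follows that section, a valid exit value precedes it and the fallback correctly selects it. This stands. A reader might infer that every use of the fallback reaches back before Maintenance, or that it should be switched off for EQ-5D-5L. The documents support neither, and switching it off would discard valid exit assessments.
- **The zero change may never arise.** Change requires a post-baseline value, and Visit 1 is the baseline. This largely answers the 4 mg case, although the selection rule itself contains no such limit. It does not answer Visit 2a, which is after baseline but before 8 mg Maintenance.
- **The specific rule may override the general one.** Section 8.2 addresses EQ-5D-5L by name, while 8.3 names carry-forward only for laboratory values, vital signs and ECGs. SAP Section 8 also leaves data handling to be settled before database lock. That is a fair reading, but the SAP does not state it.
- **Exit data should be nearly complete.** Protocol 9.5.5 requires early discontinuation procedures of everyone who discontinues, and these include EQ-5D-5L. This limits the number affected but does not remove the ambiguity.

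**Conclusion.** The concern holds in a limited form. Where the closing EQ-5D-5L was not done and no later value exists, the literal treatment-phase rule selects Visit 2a for an 8 mg subject, or Visit 1 for a 4 mg subject unless the definition of change excludes it. This conflicts with the EQ-5D-5L missing-data rule, and the SAP leaves the conflict unresolved.

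The size is small. The endpoint is exploratory and descriptive, and no primary or key secondary analysis is affected. The number of subjects cannot be derived from the documents. A reader might infer that the mean change is pulled toward zero by a known fraction. The documents do not support that: they give no rate of missing closing assessments, the zero-change case may be screened out, and a Visit 2a value is not a zero.

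Nor does the point extend to the entire-study time point as a whole. For a subject who reached the Extension Phase, that fallback can select an on-treatment value such as Visit 9, 9a or 13.

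The conclusion rests on the scheduled visits in Tables 3 to 5 and on a literal reading of SAP 8.1. An EQ-5D-5L taken outside the schedule could change which value is selected.

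**What to change.** Keep the fallback and bound it. Add to SAP 8.1: *For EQ-5D-5L, the end-of-treatment-phase value must be dated after the first dose of the Maintenance Period of the last evaluated dose and no later than the visit that closes that period (Visit 9 or 9a, early transition, early discontinuation, or Visit 2a where it closes the 4 mg Maintenance Period as last evaluated dose); otherwise it is missing.*

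The lower limit removes the pre-Maintenance selections and agrees with SAP 8.2. The upper limit keeps an Extension value such as Visit 13 from being labelled end of treatment phase. Valid closing values taken shortly before the disposition date are retained.

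State that the same rule applies to subjects still in the 8 mg Treatment Phase at the primary-endpoint analysis, and report the number with a missing value by exit reason.

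The cost is a short SAP addition, one extra count to report, and slightly fewer subjects in one exploratory table. No data collection changes.

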8.2 Efficacy Data Handling

Definition of Seizure-Free status

The definition of seizure-free for perampanel 4 mg will be as follows;

The subjects who completed the 4 mg Treatment Phase with no seizures will be treated as Seizure-Free status. The subjects who had any seizures will also be treated as Seizure-Free status only if the seizure(s) appeared after the Day 183 (ie, the target visit date of the 26th week of 4 mg Maintenance Period). Day 1 is the date of first dose of study drug in the 4 mg Maintenance Period. Otherwise, subjects will be regarded as non-Seizure-Free for the evaluation of perampanel 4 mg.

The definition of seizure-free for perampanel total (regardless of doses) will be as follows;

The subjects who completed the Treatment Phase of the last evaluated dose (ie, 4 or 8 mg) with no seizures will be treated as Seizure-Free status. The subjects who had any seizures will also be treated as Seizure-Free status if the seizure(s) appeared after the Day 183 (ie, the target visit date of the 26th week of Maintenance Period for the last evaluated dose). Day 1 here is the date of first dose of study drug in the Maintenance Period of the last evaluated dose. If subjects who were titrated up to 8 mg but down-titrated to 6 mg due to tolerability issue continued the study and completed the Maintenance Period with no seizure, those will also be treated as Seizure-Free status. Otherwise, subjects will be regarded as non-seizure-free.

Handling of seizure frequency

- **Baseline**

Baseline seizure frequency will be composed of the record based on the interview at visit 1 and the dispensed diary. Baseline seizure frequency will be calculated as the number of seizures per 12 weeks (see below).

$\frac{\text{Sum of seizures during baseline}}{\text{the number of days (84 days plus the study days during the Pretreatment Phase)}} \times 84$

Study days during the Pretreatment Phase will be the period between the date of obtaining informed consent and the date of first study drug dosing (ie, the date of study drug dispensing for visit 2).

- **Post-Baseline (Maintenance Period and Extension Phase)**

Post-baseline seizure frequency will be composed of the dispensed diary. Post-baseline seizure frequency will be calculated as the number of seizures per 12 weeks (see below). The Follow-up Phase will not be included in this analysis.

$\frac{\text{Sum of seizures during post-baseline}}{\text{the number of study days during post-baseline}} \times 84$

Study days during the post-baseline of maintenance period will be the period between the date of study drug dispensing for the Maintenance Period of the last evaluated dose and the disposition data in maintenance period of the last evaluated dose. Study days during the post-baseline of extension phase will be the period between the disposition data in maintenance period of the last evaluated dose and the date of data cutoff or the date of study discontinuation, whichever comes first.

the data on seizure expression that obtained during the Titration Period and the Follow-up Phase will be presented only in the subject data listing.

Handling of missing data

- **Seizure frequency**

If subjects have a missing seizure count in any of each seizure type (ie, simple partial with motor signs, simple partial without motor signs, complex partial, and complex partial with secondarily generalized seizure) for each unique diary record, the overall seizure frequency for that record will be handled as missing data. Similarly, if complex partial and/or complex partial with secondarily generalized seizure are missing for each unique diary record, then complex partial seizure plus secondary generalized seizure frequency will be handled as a missing data.

- **EQ-5D-5L**

No imputation will be performed for the missing value.

Censoring rules for time to event analysis

1. The censored rule for the analysis of time to first seizure onset will be provided in the following table. If subjects met multiple censoring criteria, the censoring date will be the earliest date of them.

No.	Situation	Date of Event or Censoring	Outcome
1	Seizure onset	Date of the first seizure onset	Event
2	Withdraw from the study	Date of study withdrawal	Censored
3	Ongoing at the data cutoff (with no seizure)	Date of data cutoff (each subject's final non-missing assessment date)	Censored

2. The censored rule for the analysis of time to study withdrawal will be provided in the following table. If subjects met multiple censoring criteria, the censoring date will be the earliest date of them.

No.	Situation	Date of Event or Censoring	Outcome
1	Withdraw from the study	Date of study withdrawal	Event
2	Ongoing at the data cutoff	Date of data cutoff (each subject's final non-missing assessment date)	Censored

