3.2 Overall Study Design and Plan

This study is a multicenter, uncontrolled, open-label, single-arm study in untreated patients with partial onset seizures (including secondarily generalized seizures). This study consists of a Pretreatment Phase, a Treatment Phase (a Titration Period, a Maintenance Period), an Extension Phase, and a Follow-up Phase.

Pretreatment Phase

During the Pretreatment Phase (maximally 4 weeks), patients will be screened and be

assessed for their eligibility to participate in the study.

Treatment Phase

The Treatment Phase consists of the 4 mg Treatment Phase (the Titration Period [6 weeks] and the Maintenance Period [26 weeks]) and the 8 mg Treatment Phase (the Titration Period [4 weeks] and the Maintenance Period [26 weeks]) if subjects require higher dose.

Extension Phase

When subjects complete the Treatment Phase and agree to continue receiving the perampanel monotherapy, they could enter the Extension Phase. Subjects will continue to receive perampanel until 3 or less months from the date of approval of perampanel monotherapy in each country unless subjects experience tolerability issues such as occurrence of adverse events or need to take other antiepileptic drugs (AEDs) because of insufficient efficacy of perampanel.

Follow-up Phase

Subjects who will finish or discontinue the study will conduct the follow-up visit 4 weeks after withdrawal of perampanel.

The study design is shown in [Figure 1](#).

[figure not shown]

Figure 1 Study Design

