5.4.1 Primary Efficacy Analyses

The number (percentage) of subjects with POS who achieved seizure-free during the 26-week Maintenance Period of 4 mg and the exact corresponding 95% confidence interval (CI) will be calculated on the mITT Analysis Set. The primary interest of this study will be to confirm that the exact 95% lower CI is above the pre-specified threshold (ie, 40%). If subjects experience no seizures during the 4 mg Maintenance Period, those will be regarded as seizure-free in this analysis. Otherwise, subjects will be regarded as non-seizure-free.

The definition of seizure-free status will be detailed in the [section 8](#).

SENSITIVITY ANALYSIS

Sensitivity analyses for the primary efficacy analysis will be performed on the ITT Analysis Set.

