5.4.2 Secondary Efficacy Analyses

The number (percentage) of subjects with POS who achieved seizure-free during the 26-week Maintenance Period regardless of perampanel dose and the exact corresponding 95% CI will be calculated. To examine if the 95% lower CI exceeds the threshold (ie, 40%) is the key secondary efficacy analysis. The 26-week Maintenance Period mentioned here is the Maintenance Period of the last evaluated dose (ie, 4 or 8mg).

The number (percentage) of subjects with POS who achieved seizure-free during the 52-week treatment of 4 mg (ie, 26-week Maintenance Period of 4 mg and 26-week Extension Phase) and the corresponding 95% CI will be calculated.

The number (percentage) of subjects with POS who achieved seizure-free during the 52-week treatment (ie, 26-week Maintenance Period and 26-week Extension Phase) and the corresponding 95% CI will be calculated. The 26-week Maintenance Period mentioned here is the Maintenance Period of the last evaluated dose.

Median, Q1 and Q3 time to first seizure onset will be estimated by Kaplan-Meier method. The cumulative probability of the event (ie, seizure occurrence) at every 26 weeks will also be calculated. Corresponding 2-sided 95% CIs will also be presented. Kaplan-Meier estimates of the time to event will be plotted over time. The Follow-up Phase will not be included in this analysis. The above analysis will be summarized for the entire study period of 4 mg and the entire study period of the last evaluated dose, respectively.

Time to first seizure onset will be defined as the period from the first dose of study drug in the Maintenance Period of the last evaluated dose to the first seizure onset. The censoring rule for the analysis of time to first seizure onset will be provide in the [section 8](#).

Median, Q1 and Q3 time to withdraw from the study will be estimated by Kaplan-Meier method. The cumulative probability of the event (ie, withdraw from the study) at every 26 weeks will also be calculated. Corresponding 2-sided 95% CIs will also be presented. Kaplan-Meier estimates of the time to event will be plotted over time. The Follow-up Phase will not be the period to be analyzed. The above analysis will be summarized for the entire study period of 4 mg and the entire study period of the last evaluated dose, respectively.

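### SAP 8.2 ties seizure-free status to the Treatment Phase, which includes titration, although the primary endpoint covers the 26-week Maintenance Period only

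*SAP*

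**What the plan says.** The primary endpoint (Protocol 9.7.1.1.1, SAP 5.1.1) is the seizure-free rate in the 26-week Maintenance Period. Protocol 7.2 supports that window with a guideline that leaves titration out of the evaluation. SAP 5.4.1 applies it, in the same words as Protocol 9.7.1.6.1: "If subjects experience no seizures during the 4 mg Maintenance Period, those will be regarded as seizure-free in this analysis". SAP 5.4.1 then adds "The definition of seizure-free status will be detailed in the" and points to Section 8.

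SAP 8.2 uses a different period for 4 mg: "The subjects who completed the 4 mg Treatment Phase with no seizures will be treated as Seizure-Free status". Its one exception covers seizures after Day 183, counted from the first dose in the 4 mg Maintenance Period. Everyone else is non-seizure-free. SAP 3.2, like Protocol 9.1.2, defines the term: "The Treatment Phase consists of the 4 mg Treatment Phase (the Titration Period [6 weeks] and the Maintenance Period [26 weeks"; the 8 mg Treatment Phase is 4 plus 26 weeks.

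The any-dose definition in 8.2 covers "The subjects who completed the Treatment Phase of the last evaluated dose (ie, 4 or 8 mg) with no seizures", yet its sentence on subjects reduced to 6 mg requires only that they "completed the Maintenance Period with no seizure, those will also be treated as Seizure-Free status". SAP 5.4.2 says of the key secondary analysis: "The 26-week Maintenance Period mentioned here is the Maintenance Period of the last evaluated dose (ie, 4 or 8mg". Later in 8.2, after the seizure-frequency rules, comes this: "the data on seizure expression that obtained during the Titration Period and the Follow-up Phase will be presented only in the subject data listing".

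**The concern.** SAP 5.4.1 and SAP 8.2 classify the same subject differently, and 5.4.1 names Section 8 as the place where the definition is given in detail. A programmer could reasonably code 8.2 as written.

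This rule sets the numerator that is compared with the 40% threshold in both the primary and the key secondary analysis. Literal use would lengthen the seizure-free requirement from 26 to 32 weeks at 4 mg and from 26 to 30 weeks at 8 mg. The trial would then be tested on a stricter endpoint than the one it was designed and powered for. Because the study is open-label and single-arm, the choice of reading should not be left until it is known which subjects it affects.

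**Working it through.** **1. One subject under each rule.** Take a subject with one seizure in week 4 of 4 mg titration and none in the 26 weeks of maintenance.

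| Text | Window | Result |
|---|---|---|
| Protocol 9.7.1.1.1 and 9.7.1.6.1; SAP 5.1.1 and 5.4.1 | 4 mg Maintenance Period | seizure-free |
| SAP 8.2, main clause | 4 mg Treatment Phase (6 + 26 weeks) | not met |
| SAP 8.2, exception | after Day 183 of maintenance | not met: the seizure precedes Day 1 |
| SAP 8.2, residual clause | – | non-seizure-free |

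**2. Can such a subject be in the mITT set?** Yes. Protocol 9.1.2.1 makes entry to maintenance depend on safety at the end of titration, not on freedom from seizures. The seizure-triggered rules start after Visit 4 (Table 3, footnote g) and Visit 4a (Table 4, footnote e). The mITT set (SAP 5.2.1) needs entry to 4 mg maintenance and a measurement there. No text expressly removes these subjects.

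**3. The any-dose rule.** Take two subjects whose only seizure after the switch was in 8 mg titration. The one who stays on 8 mg is judged on the Treatment Phase and fails. The one reduced to 6 mg is judged on the Maintenance Period and passes.

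**4. The plan's own figures.** Inputs from SAP Section 4: n = 72, threshold 40%, planning rate 60%, Clopper-Pearson 95% interval. The lower limit for x of n is the 2.5% quantile of Beta(x, n − x + 1).

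- 38/72: 40.65%, above 40%, passes. This agrees with the tabled 40.7%.
- 37/72: 39.31%, fails.
- Power = P(X ≥ 38 | n = 72, p = 0.60) = 91.4%, which agrees with the stated power of more than 90%.
- All tabled rows from n = 71 to 81 reproduce.
- The Day 183 cut fits the visit schedule: 225 − 43 + 1 = 183.

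**5. Effect of literal use.** Let s be the share of maintenance-seizure-free subjects who also had a titration seizure. The documents give no value, so s is an assumed range. Power = P(X ≥ 38 | n = 72, p = 0.60 × (1 − s)). The expected number reclassified is 72 × 0.60 × s.

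| s (assumed) | p | Expected number reclassified | Power |
|---|---|---|---|
| 0% | 0.600 | 0 | 91.4% |
| 2% | 0.588 | 0.9 | 87.6% |
| 5% | 0.570 | 2.2 | 80.1% |
| 10% | 0.540 | 4.3 | 62.9% |

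Power falls below 90% once s exceeds 0.8%, and below 80% once s exceeds 5.0%.

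**6. Effect on an observed result.** At 38/72, one reclassification turns a pass into a fail. At 43/72 (59.7%, close to the planning rate), five leave 38/72, which passes, and six leave 37/72, which fails.

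**The case against.** The best reply is that the context already shows a maintenance-only meaning. Completing the 4 mg Treatment Phase is a disposition category in SAP 5.2.2, so the 8.2 phrase may state a completion condition, with the seizure window supplied by 5.1.1 and 5.4.1. Day 1 in 8.2 is the first maintenance dose. The 6 mg sentence names the Maintenance Period. Titration seizure data are to appear only in a listing, which hardly fits a rule that lets them alter the primary numerator. On that reading the 8 mg/6 mg discrepancy disappears. In addition, SAP Section 8 already says that data handling is settled before database lock, derivation rules sit in separate specifications (SAP Section 9), the power losses rest on an assumed s, and any error is conservative.

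Much of this stands. Maintenance-only is probably what was meant, the discrepancy in step 3 arises only on the literal reading, the values of s are hypothetical, and the type I error does not rise. A threshold of s = 0.8% is also only about a third of a subject (72 × 0.60 × 0.008 = 0.35).

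It does not remove the defect. The Day 1 anchor dates only the Day 183 cut. The listing sentence follows the seizure-frequency rules and does not mention seizure-free status. Treatment Phase is a defined term, and no text says which section prevails. If maintenance-only was intended, the operative definition says something else and should be corrected.

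**Conclusion.** The concern holds. As written, SAP 8.2 makes a titration-only seizure a failure on an endpoint that the protocol and SAP 5.4.1 confine to maintenance, and the same wording affects the key secondary analysis. The contradiction follows from the text and needs no assumption.

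Its numerical effect is unknown, because the documents give no titration-seizure rate. It is nil if no otherwise seizure-free subject had a titration seizure. At assumed shares of 2% to 10%, power would be 87.6% to 62.9% instead of 91.4%, given the 60% planning rate and 72 mITT subjects. The direction is a lower seizure-free rate, never a false success. It should be fixed before database lock, because one subject can decide a result at the boundary.

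**What to change.** In SAP 8.2:

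- For 4 mg, require that the subject completed the 4 mg Maintenance Period with no seizures during that period.
- For the any-dose definition, require the same for the Maintenance Period of the last evaluated dose.
- Add that seizures in the 4 mg or 8 mg Titration Period do not count toward seizure-free status.
- Leave the Day 183 rule as it is.

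In SAP 5.4.1, keep no separate rule. Its present sentence has no completion requirement, so leaving it beside 8.2 would preserve two definitions. State there only that status is determined by 8.2, including for non-completers and for ITT subjects who never enter maintenance, who are non-seizure-free.

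The cost is SAP wording, with no new data and no new analysis. Compared with literal use of 8.2, only subjects whose sole disqualifying seizures were in titration change class, and that restores the protocol's endpoint.
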